12.7 Safety evaluation

Safety evaluation will include assessment of AEs, vital signs, ECG, physical examination data and laboratory assessment in the safety population. All safety statistical analyses will be performed descriptively.

AEs/ADRs/SAEs will be analyzed descriptively, the evaluation of adverse events will comprise various frequency tabulations by system organ class and preferred term coded according to MedDRA. The AEs will be will be tabulated for each treatment group separately on a patient basis (counting each preferred term once per patient). Descriptive statistics will be also tabulated by relation to study drugs and severity by treatment group. The tables for AEs will present the number of patients with an event within each preferred term as a percentage of the number of treated patients. The number of events within each preferred term will also be reported. For each patient and each adverse event, the worst severity category recorded will be used in the by-severity summaries. The worst causality category (most related to treatment) will be used in the by-causality summaries.

Blood count, biochemistry and urinalysis data as well as change from baseline in laboratory data will be tabulated descriptively by treatment group and by visit. Frequency tables of laboratory shifts with respect to the reference range will also be presented. Clinically relevant abnormalities will be listed individually.

Vital signs data and change from baseline values will be summarized descriptively by treatment group and by visit.

The baseline and postbaseline ECG as well as physical examination data will be summarized descriptively by visit and by treatment group.

12.8 Pharmacokinetic parameters

The non-compartment method will be used to analyze the Nemonoxacin concentration-time data after the first intravenous infusion in adult patients with CAP.

The following pharmacokinetic parameters will be estimated from the measured concentrations: the peak drug concentration (C_{max}), 22.5-h drug concentrations ($C_{22.5h}$), areas under the concentration-time curve from 0 to 22.5 h, and 0 h to infinity ($AUC_{0-22.5}$, $AUC_{0-\infty}$), total systemic clearance (CL), volume of distribution at steady state (V_{ss}), and terminal elimination half-life ($T_{1/2}$).

Plasma concentrations will be plotted graphically versus time for all subjects on both linear and semilogarithmic scales. The mean profile will also be presented. The planned blood sampling times will be used for PK concentration summaries and plots. The actual sampling times will be recorded and used for determination of pharmacokinetic parameters.

Descriptive summary will be provided for the plasma concentration-time data of each time point and for the calculated PK parameters.

CONFIDENTIAL Page 67 of 88

12.9 Procedures for reporting any deviations from the original statistical plan.

The statistical analysis will be performed under supervision of the responsible biostatistician. The statistical analysis will be described in detail in the statistical analysis plan in accordance with GCP requirements and other applicable requirements and laws. The statistical analysis plan will be finalized prior to the database close-out. All deviations from the original statistical analysis plan will be justified in the final clinical study report.

12.10 Sample size calculation

The primary efficacy objective is to show that Nemonoxacin is not inferior to Levofloxacin (Tavanic[®]) for the treatment of CAP, on the basis of the primary efficacy endpoint - clinical success at Visit 4 (Test of cure visit) in the mITT population. The sample size calculation for this endpoint is based on assuming a clinical success rate of 82% in the treatment and in the active control group, and an eligibility of 80% of the randomized patients for mITT population. Non-inferiority margin is chosen to be 15% (i.e., δ = -15%), a one-sided significance level α is set at 5%. Then, to achieve power of 80%, the sample size for equal allocation is estimated as 171 randomized patients in each group (342 patients totally) that provides about 137 patients in each group (274 patients totally) in the mITT population.

Presumably screening of 382 patients will allow enrollment and randomization of 342 patients.

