12.4 General considerations

Demographic and clinical characteristics at baseline, medical history, efficacy and safety data will be summarized using descriptive statistics by treatment group and by time point of assessment.

Continuous data will be summarized in terms of the mean, standard deviation (SD), median, 25th and 75th percentile, minimum, maximum and number of observations. In general, categorical and ordinal data will be summarized in terms of the frequency and percentage in each category.

Using explorative methods, both treatment groups will be analysed for homogeneity on the basis of patient's baseline characteristics. Analysis of variance (ANOVA) or Wilcoxon-Mann-Whitney test, as appropriate, will be used to test and compare the continuous demographic and baseline characteristics between treatment

CONFIDENTIAL Page 64 of 88

groups. The Pearson χ^2 (or Fisher's exact test) will be used to perform between-group comparisons on categorical and binominal demographic and baseline data.

Medical history will be coded using the Medical Dictionary for Regulatory Activities (MedDRA) version 17.1. The prior and concomitant medication will be coded using World Health Organization (WHO) Drug Dictionary (version 2013-12-19), including ATC code.

For the primary efficacy endpoint, the non-inferiority hypothesis will be tested at one-sided 0.05 significance level. For other statistical analyses statistical significance will be declared at the 2-sided 0.05-level, unless otherwise specified.

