12.6.2 Primary efficacy analysis

The percentage and the number of patients with different categories of clinical response ("clinical success", "clinical failure", "indeterminate") will be summarized by treatment group in mITT and CE populations for Visit 2 (switch to oral therapy), Visit 3 and Visit 4.

The percentage of patients with clinical success (as judged by the investigator) at the test of cure Visit 4 is defined as primary endpoint variable.

In regards to efficacy for CAP, non-inferiority of Nemonoxacin compared to Tavanic[®] will be evaluated for clinical response by using a one-sided 95% confidence interval for the difference in the primary efficacy endpoint (investigational drug minus comparator). Non-inferiority of Nemonoxacin will be stated if the lower boundary of the estimated one-sided 95% confidence interval for the difference in the clinical success rate of Nemonoxacin and Tavanic[®] is above -15% the Farrington-Manning test.

CONFIDENTIAL Page 65 of 88

The primary analysis will be performed in the mITT population.

If non-inferiority is shown, a test on superiority will be performed in addition using the two-sided 95% confidence interval. The test on superiority is significant, if the lower two-sided 95% confidence interval limit is above "0".

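### The stated inputs need about 84 evaluable patients per group, not 137; with 137 the power is about 94%, not 80%

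*Combined protocol and SAP*

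**What the plan says.** Section 12.10 sizes the trial on clinical success at the test of cure visit in the mITT population, "assuming a clinical success rate of 82% in the treatment and in the active control group". It sets the margin at 15 percentage points, the significance level at one-sided 5% and the mITT share at 80% of randomised patients. It then states that "to achieve power of 80%, the sample size for equal allocation is estimated as 171 randomized patients in each group" and "that provides about 137 patients in each group (274 patients totally) in the mITT population". The Synopsis gives the same calculation.

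The analysis sections agree with these inputs. Section 12.4 says "the non-inferiority hypothesis will be tested at one-sided 0.05 significance level". Section 12.6.2 requires that the lower confidence bound "is above -15% the Farrington-Manning test". No assumed true difference other than zero is given, and no inflation factor beyond the 80% mITT share. Section 12.10 names no sample-size formula.

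**The concern.** With equal success rates of 82% and a margin as wide as 15 points, 137 evaluable patients per group is far more than 80% power at one-sided 5% would normally need. Section 12.10 presents the number as what the inputs require. It does not describe a deliberately larger trial and gives no reason for extra patients.

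The calculation therefore cannot be checked by a reader, an ethics committee or a regulator. If the real calculation used another level or margin, the trial was sized for a decision rule other than the one in 12.4 and 12.6.2. If it assumed unequal success rates, the planning assumption is misreported.

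**Working it through.** **Inputs.** Success rate 0.82 in each group, margin 0.15, one-sided level 0.05, power 0.80, 1:1 allocation, mITT share 0.80 (all 12.10; level confirmed in 12.4, margin and test in 12.6.2). Normal quantiles: 1.645 and 0.842.

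**The plan's own figure.** 171 × 0.80 = 136.8, which is the stated 137 to rounding. Working back, 137 / 0.80 = 171.25. The inflation step is sound, so the question is how 137 was reached.

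**Unpooled normal approximation.** n = (1.645 + 0.842)² × 2 × 0.82 × 0.18 / 0.15² = 81.1, so 82 per group.

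**Farrington-Manning.** The success rates restricted to a difference of −0.15 are 0.723 and 0.873.

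- Null standard deviation term: √(0.723 × 0.277 + 0.873 × 0.127) = 0.557
- Alternative term: √(2 × 0.82 × 0.18) = 0.543
- n = [(1.645 × 0.557 + 0.842 × 0.543) / 0.15]² = 83.9, so 84 per group

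**Variants at one-sided 5% and 80% power.** The continuity correction is n/4 × (1 + √(1 + 4/(0.15n)))². Randomised numbers are n/0.80, rounded up.

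| Method | Evaluable per group | Randomised per group |
|---|---|---|
| Unpooled | 82 | 103 |
| Farrington-Manning | 84 | 105 |
| Unpooled, continuity-corrected | 95 | 119 |
| Farrington-Manning, continuity-corrected | 97 | 122 |
| Pooled superiority form, 82% vs 67% | 104 | 130 |
| Same, continuity-corrected | 117 | 147 |
| **Stated in 12.10** | **137** | **171** |

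The last two variants solve a different problem (detecting a 15-point difference) and are included only to widen the search. Even the largest is 20 short of 137.

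**Power at 137 per group under the stated inputs.**

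- Unpooled: standard error √(2 × 0.82 × 0.18 / 137) = 0.0464; 0.15 / 0.0464 − 1.645 = 1.587, so power is 94.4%.
- Farrington-Manning approximation: (0.15 × √137 − 1.645 × 0.557) / 0.543 = 1.544, so power is 93.9%.
- Exact power of the Farrington-Manning test by full binomial enumeration: 94.1%. The same enumeration gives 80.0% at 82 per group (0.7999 before rounding) and 80.6% at 84.

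**Could attrition explain the gap?** No. Going from 84 evaluable to 171 randomised would need an mITT share of 84 / 171 = 49%, against the stated 80%.

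**What does give about 137?** Only a changed input. Three examples, none documented:

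- 79% vs 82% at 5% and 80% power: Farrington-Manning 137.0.
- 82% in both groups at one-sided 2.5% and 90% power: unpooled 137.9.
- 50% in both groups at 5% and 80% power: unpooled 137.4.

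These show that several different calculations lead to the same neighbourhood. They are not evidence for any one of them.

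**The case against.** The best counter-argument is that nothing is at risk. Under the stated inputs the trial is larger than it needs to be, so the primary test keeps its level and has more power than claimed. The margin and the level are the same wherever they appear, so nothing positively suggests that a different decision rule was intended. On this view the point is a reporting slip. The absence of harm under the stated inputs stands, and it limits the severity. It does not make the statement correct: 12.10 gives 171 as the number needed for 80% power, and it is not.

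A second objection is that the 80% may be right and one of the inputs misprinted. That also stands as a possibility, and it is why restating the power is the correct remedy only if the printed inputs are the intended ones.

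A third is that the size of the excess depends on the formula, since 12.10 names none. That is fair: 137 is 63% above 84, 41% above the continuity-corrected 97, and 17% above the least favourable variant (117). The conclusion is the same in each case.

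Finally, any list of alternative inputs is speculative, and strict rounding up of the three examples gives 172 or 173 randomised rather than 171. That is a good reason not to adopt one of them after the fact.

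**Conclusion.** The concern holds. The sample size in 12.10 and the Synopsis cannot be reproduced from the inputs given there. Those inputs need 84 evaluable patients per group by the plan's named test (82 unpooled), or 105 (103) randomised per group and 210 (206) in total, against the stated 137, 171 and 342. At 137 per group the power is 93.9% to 94.4% (exact 94.1%), not 80%.

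This rests only on figures in the documents. It assumes that the 82% rates, the 15-point margin and the one-sided 5% level are as printed. Whether the error is in the 137 or in a printed input cannot be settled from the documents. Under the printed inputs it is conservative and leaves the validity of the primary analysis untouched. It should be fixed because the stated justification for the trial's size is wrong as written.

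**What to change.** Do one of the following in 12.10 and the Synopsis.

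1. If the printed inputs are the intended ones, keep them and the sample size, and state that 137 evaluable patients per group give about 94% power. This is one corrected sentence in each of two places, with no change to the number of patients, the test, the margin or the level.
2. Otherwise, state the success rates, margin, level, power, formula and software actually used. If the level or margin differs from what is printed, reconcile 12.4 and 12.6.2, and the matching Synopsis text, so that the sizing and the decision rule agree.

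The choice must come from the sponsor's record of the original calculation, not from picking inputs that happen to return 137. If the correction is made as a protocol amendment, section 13 requires ethics committee approval.

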13 ETHICAL AND LEGAL CONSIDERATIONS

The study will be conducted in accordance with the principles of the World Medical Association Declaration of Helsinki, Good Clinical Practice of the International Council on Harmonisation (ICH GCP) and all requirements of the local national legislation.

The clinical study will be conducted in accordance with the Protocol. Protocol, as well as the patient information and informed consent form will be approved/endorsed by the Institution Review Board/ Independent Ethics Committee before the start of the study.

The Protocol amendments should also be approved/endorsed by the Institution Review Board/ Independent Ethics Committee.

13.1 Informed Consent Form

Before enrollment into the study the patient or his legal representative are provided with oral information and written materials about the aims and methods of the study, as well as the anticipated benefits and possible risks associated with participation in the study. In addition, the patient or his legal representative should be notified of the voluntary nature of participation in the study and that the patient has the right to refuse to participate in the study at any time, and this refusal will not affect the quality of medical

CONFIDENTIAL Page 68 of 88

care provided to him/her. Although the patient is not obligated to disclose his reasons to interrupt the participation in the study, the investigator should try to find out the reasons, without violating the rights of the patient of the study. Written consent of the patient should be obtained before conducting any research procedures, the second original and signed copy of the Informed Consent Form is handed to the patient.

Processing of data collected in the course of the study is carried out in compliance with confidentiality of study patients. Patients should be informed about the purpose of the planned data processing and the terms of the publication of these data (e.g., for presentation at medical conferences). The patient or his legal representative must provide consent for the data processing and publication of information in case it does not identify his/her personality.

Patients should be made aware that the authorized representatives of health authorities and the sponsor have access to their confidential medical information for purposes of audit. Patients or their legal representatives should provide written consent for the access to this information by these persons. However, in this case patients should be guaranteed strict confidentiality of all information which may identify patient and non-disclosure of such information.

13.2 Information Confidentiality

The information contained herein is the property of the Sponsor and transfer to third parties is allowed only with written permission from the Sponsor. The right to become acquainted with this information is granted only to the investigator(-s) and the staff of the research center(-s) participating in the study, members of an Ethics Council and health care officials, authorized to monitor the trial conduct. Information about the study to the extent necessary for making a decision on granting consent to participate is provided to patients whom the investigator plans to treat with the investigational drug.

13.3 Financing and Insurance coverage

This study is sponsored and financed by R-Pharm JSC. The Study Sponsor R-Pharm JSC has concluded a license agreement with the manufacturer of the investigational product TaiGen Biotechnology Co. Ltd., according to which R-Pharm JSC is entitled to perform development, registration, and commercial promotion of the medicinal product Nemonoxacin.

The insurance against the risk of life and health injury is guaranteed to the patients participating in clinical study. The investigator should inform the patient about the provision of such insurance, as well as to explain to the patient that the conduct of other forms of treatments and concomitant therapy during the study (except emergency care) is possible only with the permission of the investigator.

All risks associated with the conduct of this clinical study are insured by 'Alliance Insurance Company' OJSC in accordance with the current legislation (Federal Law No. 61 "On the circulation of medicinal products" and Decree No. 714 of the Government of the Russian Federation dated 13 September 2010 "On approval of the typical rules for mandatory insurance of the life and health of patients participating in clinical studies of medicinal products").

CONFIDENTIAL Page 69 of 88

14 ADMINISTRATIVE OBLIGATIONS

14.1 Data collection

All clinical data will be documented in the eCRF after recording in the source documents. The investigator is responsible for ensuring that all sections of the eCRF are completed correctly and that the entries can be verified against source data whenever applicable.

14.2 Data handing

After completion of data entry checks for plausibility, consistency, and completeness of the data will be performed. All missing data or inconsistencies will be reported back to the site as queries and clarified by the responsible person. If no further corrections are to be made in the database it will be declared closed and used for statistical analysis.

All data management activities will be done according to the current Standard Operating Procedures (SOPs) of the OCT.

14.3 Storage and archiving of Data

According to the regulations all important trial documents (e.g. eCRF) will be archived for at least 15 years after the final study termination. Before disposing of any documents the investigational site should contact the Sponsor and receive written approval for disposal of the documents.

The Sponsor is responsible for archiving of trial master file including all essential trial documents. Furthermore, the Principal Investigator will archive all trial-specific data (source data and Investigator Site File (ISF) including participant identification list and relevant correspondence).

15 QUALITY CONTROL AND QUALITY ASSURANCE

The representative of the sponsor/CRO (the CRA) together with the investigators and staff of the site will conduct the discussion of the Protocol and eCRF prior at the beginning of the study during the initiating visit in the site and/or at an investigators' meeting. During the study the CRA will regularly attend the site and check the completeness of source documentation and accuracy of patient records in eCRF (100% source data verification), the implementation of protocol requirements and Good Clinical Practice, the course of patient recruitment into the study, as well as conditions of study medication storage, dispense and accounting. During these visits the core investigational staff should provide the CRA with necessary assistance.

The investigator should store the source documentation for each patient

CONFIDENTIAL Page 70 of 88

participating in the study which contains the patient's personal data of (hospitalization and medical history), and notes made during visits, including demographic and medical information, lab tests data and all other tests and procedures. Any information that the eCRF contains should have the original source in the source documents. The investigator also should store the original Informed Consent Form signed by the patient.

The investigator must provide the CRA an access to all the patients' source documents to confirm the accuracy of the data entered in the eCRF. No source document that identifies the patient's personality is to be disclosed.

The representatives of the Sponsor should be given an opportunity to conduct periodic visits to all the sites involved in the study to test the quality of the study. At site they will check records on the study and compare them with the source documents as well as discuss the course of the study with the investigators and check if the equipment complies with the Protocol.

In addition, the study may be inspected by the internal auditors of the Sponsor and persons authorized by the Sponsor, as well as by state inspectors, who should be granted an access to eCRFs, source documents, other study files and research equipment. Audit reports from the Sponsor are confidential.

16 PUBLICATIONS

The clinical study center is not allowed to publish the trial results without obtaining an approval by the sponsor.

CONFIDENTIAL Page 71 of 88

APPENDIX 1: CRITERIA FOR HOSPITALIZATION*

Criteria for hospitalization in patients with a confirmed diagnosis of community-acquired pneumonia*

Patients require hospitalization if they comply with **at least one** of the following criteria:

- 1. Physical examination data:
 - Respiratory rate \geq 30 breaths per minute
 - Diastolic blood pressure ≤60 mm Hg
 - Systolic blood pressure <90 mm Hg
 - Heart rate ≥125 beats per minute
 - Temperature < 35.5°C or ≥ 39.9 °C
- 2. Laboratory data and X-ray findings:
 - WBC count of $< 4.0 \times 10^9 / L$ or $> 20.0 \times 10^9 / L$
 - SaO₂ <92% (measured by pulse oximetry)
 - PaO₂ <60 mm Hg and/or PaCO₂ >50 mm Hg while breathing room-air
 - Serum creatinin >176.7 μ mol/l or blood urea nitrogen >7.0 mmol/l (blood urea nitrogen = urea, mmol/l/2.14)
 - Pneumonic infiltration, involving more than one lobe
 - Cavitation in a lung
 - Pleural effusion
 - Rapid progression of focal-infiltrative lesions in the lungs (> 50% increasing of infiltration size within the previous 2 days)
 - Hematocrit <30% or hemoglobin <90 g/l
 - Extrapulmonary site of infection (meningitis, septic arthritis and other)
 - Sepsis or multiple organ failure, manifested as metabolic acidosis (pH <7.35), coagulopathy
- 3. Impossibility of adequate care and fulfillment of all medical prescriptions at home

Criteria for preferred inpatient treatment for patients with a confirmed diagnosis of community-acquired pneumonia*

Preferred in-patient treatment may also be considered in the following cases:

- 1. Older than 60 years of age
- 2. Concomitant diseases (chronic bronchitis, chronic obstructive pulmonary disease, bronchiectasis, malignancies, diabetes mellitus, chronic renal insufficiency, congestive cardiac failure, chronic alcoholism, drug abuse, significant weight deficit, cerebrovascular diseases)
- 3. Treatment failure after starting treatment with antibiotics
- 4. The desire of the patient and/or his/her family.

CONFIDENTIAL Page 74 of 88

Criteria for Intensive Care Unit treatment for patients with a confirmed diagnosis of community-acquired pneumonia**

The patients require hospitalization in an intensive care unit (in that case the patient will not be enrolled in the study) **if one of** the following major criteria is met:

- Severe respiratory insufficiency requiring mechanical ventilation;
- Septic shock requiring the administration of vasopressors;

OR if the patient meets **three** of the following minor criteria at the same time:

- Respiratory rate \geq 30 breaths per minute;
- Multilobar pneumonic infiltration;
- Impairment of consciousness;
- Uraemia (residual urea nitrogen $\geq 20 \text{ mg/dL}$);
- Leukopenia (white blood cell count $< 4 \times 10^9/L$);
- Thrombocytopenia (platelet count $< 100 \times 10^{12}/L$);
- Hypothermia (< 36 °C);
- Hypotension requiring intensive infusion therapy.

CONFIDENTIAL Page 75 of 88

^{*}Чучалин А.Г., Синопальников А.И. и соавт. Внебольничная пневмония у взрослых: практические рекомендации по диагностике, лечению и профилактике, пособие для врачей, Москва, 2010 (with modifications)

^{**}Чучалин А.Г., Синопальников А.И. и соавт. Клинические рекомендации по диагностике, лечению и профилактике тяжелой внебольничной пневмонии у взрослых, 2014

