7 SELECTION OF STUDY POPULATION

7.1 Inclusion Criteria

Patients will be eligible for inclusion in the study only if all of the following inclusion criteria are applied:

- 1. Written informed consent obtained from the patient.
- 2. Female and male patients aged between 18 and 70 years inclusive.
- 3. Patients with moderate to severe community-acquired pneumonia who need inpatient treatment (correspondence to at least one of the criteria for hospitalization / preferred hospitalization described in the Appendix 1 of this protocol) but do not need ICU treatment (in case of correspondence to at least one «major» or three «minor» criteria for hospitalization in intensive care unit described in Appendix 1 of this protocol, patient should not be enrolled in the study).
- 4. The presence of at least 3 of the following symptoms/signs:
 - Cough
 - Purulent sputum production
 - Tachypnea (respiratory rate > 24 breaths/minute)
 - Chills
 - Fever (rectal/ tympanic temperature $\geq 38.5^{\circ}\text{C}$ or axillary/ oral/ cutaneous temperature $\geq 38.0^{\circ}\text{C}$)
 - WBC count of $\ge 10.0 \text{ x } 10^9/\text{L}$ or $\ge 15\%$ immature neutrophils (bands; regardless of peripheral WBC count).
- 5. Radiological evidence of (a) new infiltrate(s) consistent with bacterial pneumonia at baseline.
- 6. Treatment-naive patients or patients who have received single dose of a short-acting antibacterial drug within 24 hours of enrollment or patients with treatment failure who have received antibiotics (with the exception of quinolones or fluoroquinolones) for less than 72 hours.
- 7. Consent to use contraception during participation in the study (for women childbearing potential and men).

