10.3.5 Biochemical assay

Blood samples for biochemical assay will be withdrawn before treatment initiation on Day 1 of the study (Visit 1, screening procedures), before dosing on Day 4(8) of the study (Visit 2, switch to oral therapy), within 1-2 days (Visit 3) and within 7-9

CONFIDENTIAL Page 56 of 88

days (Visit 4) after the last dose. At Visits 1, 2, and 3, samples will be collected prior to dosing.

To evaluate the selection criteria of the study, the Investigator may use blood chemistry test results obtained at the laboratory of the investigational site within 24 hours of study enrollment (Signing of the Informed Consent Form) if he / she considers that available data are sufficient to permit a decision on whether the subject meets the selection criteria. In this case, another blood sampling procedure has to be conducted in the period from the signing of the Informed Consent Form to the start of treatment in order to evaluate all other blood chemistry test parameters that have to be determined on Day 1 in accordance with the study protocol.

Biochemical assay will be performed in the local laboratory of investigational site using standard validated methods. The following investigations will be made:

- glucose
- total bilirubin
- alanine aminotransferase (ALT)
- aspartate aminotransferase (AST)
- gamma-glutamyl transpeptidase (GGTP)
- alkaline phosphatase (ALP)
- potassium (K⁺)
- sodium (Na⁺)
- creatinine
- urea.

All clinically significant abnormal changes in biochemical parameters from the baseline results must be reported as AEs in the eCRF.

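### Two eligibility thresholds in Appendix 1 are wrong as printed: the ICU platelet limit has the wrong exponent, and the ward urea line applies a mass ratio to mmol/L; the practical impact is low

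*Combined protocol and SAP*

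**What the plan says.** Section 7.1, inclusion criterion 3, makes Appendix 1 operative in two directions. The patient must show "correspondence to at least one of the criteria for hospitalization / preferred hospitalization described in the Appendix 1 of this protocol", and is not to be enrolled "in case of correspondence to at least one «major» or three «minor» criteria for hospitalization in intensive care unit".

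Appendix 1 has eight ICU minor criteria. Three of them matter here:

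- Platelets: "Thrombocytopenia (platelet count $< 100 \times 10^{12}/L".
- White cells, the line directly above: "Leukopenia (white blood cell count $< 4 \times 10^9/L".
- Urea nitrogen: "Uraemia (residual urea nitrogen $\geq 20 \text{ mg/dL".

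The ward list has a line that is met by raised creatinine or by "blood urea nitrogen >7.0 mmol/l (blood urea nitrogen = urea, mmol/l/2.14". A separate list of reasons for preferring inpatient care also satisfies criterion 3, and it includes "The desire of the patient and/or his/her family".

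Section 10.3.5 says "Biochemical assay will be performed in the local laboratory of investigational site using standard validated methods". The panel there contains urea, not urea nitrogen. Section 12.1 defines the mITT population, on which the primary analysis is run, partly by having met inclusion criteria 3 and 4.

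**The concern.** A platelet count of 100 × 10^12/L does not occur. A limit set there separates nobody from anybody, and it gives every patient one of the three minor criteria that together bar enrolment.

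The urea line has a different fault. Dividing by 2.14 turns a mass of urea into a mass of urea nitrogen, but the line applies the division to a concentration in mmol/L. Because laboratories report urea, a site that relies on this line has to use the printed conversion, and then works with a cut-off far from the one the line appears to state.

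At stake is whether eligibility can be applied as written by sites, monitors and whoever programs the analysis populations. Criterion 3 is both an entry rule and part of the mITT definition. Section 12.2 also counts enrolment of an ineligible patient as a protocol violation, which removes the patient from the CE population.

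**Working it through.** **Platelets**

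Inputs: the printed limit of 100 × 10^12/L and the 10^9/L unit of the adjacent white-cell line, both from the ICU list in Appendix 1; the rule of three minor criteria, from Appendix 1 and Section 7.1.

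1. Printed limit in the usual unit: 100 × 10^12/L = 100,000 × 10^9/L.
2. Ratio to the same figure in 10^9/L: 10^12 / 10^9 = 1000.
3. Suppose human counts run up to about 2,000 × 10^9/L (an assumption, not a figure from the protocol). The printed limit is then 100,000 / 2,000 = 50 times the top of that range, so every patient is below it.
4. Literal effect on the ICU rule: 3 criteria needed − 1 always met = 2 others. A respiratory rate of at least 30 together with multilobar infiltration would be enough. Each of those is also a ward criterion in the same appendix.

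**Urea**

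Inputs: the ward limit of 7.0 mmol/L, the divisor 2.14 and the ICU limit of 20 mg/dL, all from Appendix 1. Molar masses are standard constants: urea 60.06 g/mol; the two nitrogen atoms in one molecule 28.01 g/mol.

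1. Reproduce the divisor as a mass ratio: 60.06 / 28.01 = 2.14. It matches.
2. Try it in molar units. One molecule of urea carries one unit of urea nitrogen, so the divisor is 1. Counting nitrogen atoms instead gives a divisor of 0.5. Neither gives 2.14.
3. Cut-off with the printed conversion: urea / 2.14 > 7.0, so urea > 7.0 × 2.14 = 14.98 mmol/L. As urea nitrogen this is 14.98 × 28.01 / 10 = 42.0 mg/dL.
4. Cut-off with the molar divisor of 1: urea > 7.0 mmol/L, which is 7.0 × 28.01 / 10 = 19.6 mg/dL urea nitrogen.
5. Size of the shift: 14.98 / 7.0 = 2.14.
6. Context from the ICU list: 20 mg/dL urea nitrogen = 200 / 28.01 = 7.14 mmol/L urea. The ward cut-off as printed is 14.98 / 7.14 = 2.10 times this.
7. Worked case, urea 10 mmol/L: 10 / 2.14 = 4.67, so the ward line is not met as printed; 10 × 28.01 / 10 = 28.0 mg/dL, so the ICU uraemia line is met.

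**The case against.** The arithmetic is hard to dispute, so the case on the other side concerns weight.

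- **The platelet intention is plain.** The criterion is headed as thrombocytopenia, and no clinician would score a normal count that way. The description of Amendment No. 4 adds that the ICU list was aligned with named society criteria. This stands: sites probably apply 10^9/L already, and the loss of one criterion from the bar arises only under a literal reading.
- **A reader might infer that a ward limit above the ICU limit proves the urea line wrong.** It does not. The same appendix has a temperature pair ordered the same way: below 35.5 °C on the ward list, below 36 °C on the ICU list. The lists come from different guidelines and work differently, since one ward criterion suffices while three ICU minor criteria are needed. The error is the invalid conversion; the ICU limit is context.
- **The urea line rarely decides anything.** Multilobar disease, pleural effusion, age over 60 or a wish for inpatient care is each enough. This stands. Exclusion criterion 12 also removes many patients whose urea is raised for renal reasons.
- **A reader might infer that the wrong patients are enrolled or that the comparison is biased.** The documents support neither. Eligibility is settled before randomization, so misapplication falls on both arms alike, and nothing shows how many patients are affected.
- **A reader might infer that mITT will be distorted.** That needs the literal platelet limit to be used in the derivation, and the ICU bar to count as part of the minimal disease criteria, a phrase that suggests a lower bound on severity. Section 12.1 cites criterion 3 without separating its two halves, so the risk is open but conditional.
- **The replacement urea value is not documented.** The ward list is described as modified from its source, so 7.0 mmol/L urea is an inference. This also stands.

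**Conclusion.** Both lines are wrong as written, and the practical impact is low.

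The platelet line is the main point. Its limit is 1000 times too high, and read literally it lowers the bar to enrolment from three minor criteria to any two others. The urea line is secondary: a conversion that is invalid in its stated unit moves the cut-off from 7.0 to 14.98 mmol/L urea. The protocol's text settles that both errors exist. It does not settle the sponsor's intended urea cut-off; 7.0 mmol/L is only the value consistent with the stated urea nitrogen limit in molar terms.

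This rests on standard molar masses, on platelet counts never approaching 100,000 × 10^9/L, and on the printed exponent not being an artefact of the electronic copy. The 10^9 on the line above makes an artefact unlikely. No bias between arms, effect on the primary result or number of affected patients is shown, and none is claimed.

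**What to change.** In the next protocol amendment:

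1. Change the platelet criterion to < 100 × 10^9/L.
2. Delete the division by 2.14 from the ward line and state the limit as urea in mmol/L. The chemically consistent value is > 7.0 mmol/L. The sponsor should confirm the intended cut-off against the guideline that the ward list cites.
3. As a convenience, print 7.14 mmol/L urea beside the ICU limit of 20 mg/dL.
4. State in the statistical analysis plan, before database close-out, that the corrected limits are used when checking criterion 3 for mITT. This step applies even if enrolment has ended.

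The cost is two corrected lines and one added equivalent, ethics committee approval or endorsement under Section 13, and a notice to sites. It needs no extra patients or data and can be bundled with other changes.
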